4.5.2.4 PARTICIPANT CLASSIFICATION FOR NAb AGAINST EFGARTIGIMOD

All ADA confirmed positive samples will also be evaluated in the NAb assay. All samples that were not analyzed in the NAb assay (ie, the ADA negatives) are per default NAb negative. Also, if a NAb sample is not reported, the NAb sample status is NAb unevaluable.

For NAb against efgartigimod, all samples evaluated in this NAb assay will be scored as NAb positive or NAb negative by the laboratory. Based on these results, the subjects will be categorized based on their baseline and post-baseline sample status as detailed in following table.

Participant NAb classification	Highest ^a post baseline NAb sample status		
	NAb negative	NAb positive	NAb not evaluable
Baseline NAb sample status			
NAb negative	baseline neg – post-baseline neg	baseline neg – post-baseline pos	NAb unevaluable
NAb positive	baseline pos - post-baseline neg	baseline pos – post-baseline pos	NAb unevaluable
NAb not evaluable	NAb unevaluable	NAb unevaluable	NAb unevaluable

^a Highest sample status in order: (from low to high): NAb unevaluable, NAb negative, NAb positive.

NAb unevaluable participant = participant classified as NAb unevaluable or with missing baseline NAb sample or without post-baseline NAb samples

In case no NAb data is available at all, the participant can not be classified.

NAb incidence = percentage of participants with participant classification ‘baseline neg – post-baseline pos’ and ‘baseline pos – post-baseline pos’ (denominator: number of evaluable participants).

NAb prevalence = percentage of participants with participant classification ‘baseline neg – post-baseline pos’, ‘baseline pos – post-baseline pos’ or ‘baseline pos – post-baseline neg’ . (denominator: number of evaluable participants).

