4.5 IMMUNOGENICITY

4.5.1 Available data

Blood samples will be collected to assess the serum levels of ADA against efgartigimod and plasma levels to assess antibodies against rHuPH20. Sampling will be done predose on IMP administration visits.

Immunogenicity samples are analyzed in a 3-tiered approach:

- All samples are evaluated in the efgartigimod ADA or anti-rHuPH20 Ab screening assay and are scored screening positive or negative
- If a sample scored screening positive, it is further evaluated in the confirmatory assay and is scored confirmed positive (positive immunodepletion) or confirmed negative (negative immunodepletion).
- If a sample is scored as confirmed positive, the samples are further characterized in the titration assay (to determine titer) and are also further analyzed in the NAb (neutralizing antibodies) assay to confirm neutralizing activity. For NAb against efgartigimod, a screening assay is performed and results will be reported as negative or positive. For NAb against rHuPH20, the same 3-tiered approach is implemented: the screening NAb assay, followed by a NAb confirmatory assay, and a titer NAb assay. .

[figure not shown]
If available, a titer result will be reported for the confirmed positive samples.

However, a titer result is not always available:

- In case the confirmed positive sample could not be run in the titration assay (eg, due to insufficient sample volume/quality to perform the titer analysis), the result will be described as 'positive immuno-depletion' and the sample should be considered as positive.
- If a sample is negative in the titration assay, it will be reported as 'negative titer' but it should be considered as positive since it was confirmed positive in the second tier.
- If a sample could not be analyzed or reported as 'positive screen', the sample status is unevaluable.

An overview of this 3-tiered approach and all possible sample results that will be reported by the laboratory is given below. From these reported efgartigimod or anti-rHuPH20 Ab sample results a final ADA sample status needs to be derived during the statistical analysis, as presented in the final column ('Final Outcome'):

SGS	Statistical Analysis Plan	
ARGX-113-2002	Final Analysis	Final 5.0 of 31Jan2025

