4.5.2.5 PARTICIPANT CLASSIFICATION FOR NAb AGAINST RHUPH20

All rHuPH20 Ab confirmed positive samples will also be evaluated in the rHuPH20 NAb assay. All samples that were not analyzed in the rHuPH20 NAb assay (ie, the rHuPH20 Ab negatives) are per default rHuPH20 NAb negative. Also, if a rHuPH20 NAb sample is not reported, the rHuPH20 NAb sample status is rHuPH20 NAb unevaluable.

For NAb against rHuPH20, all samples evaluated in this NAb assay will be reported by the lab and scored as per Section 4.5.1. Based on these results, participants will be categorized based on their baseline and post-baseline sample status as detailed in following table.

	Statistical Analysis Plan	
ARGX-113-2002	Final Analysis	Final 5.0 of 31Jan2025

Participant rHuPH20 NAb classification	Highest ^c post baseline sample status			
	rHuPH20 NAb negative	rHuPH20 NAb positive (missing titer ^a)	rHuPH20 NAb positive ('negative titer' ^b or numeric titer value)	rHuPH20 NAb not evaluable
Baseline rHuPH20 NAb sample status				
rHuPH20 NAb negative	rHuPH20 NAb negative	Treatment Induced rHuPH20 NAb	Treatment Induced rHuPH20 Nab	rHuPH20 NAb unevaluable
rHuPH20 NAb positive (missing titer^a)	Treatment Unaffected rHuPH20 NAb	rHuPH20 NAb unevaluable	rHuPH20 NAb unevaluable	rHuPH20 NAb unevaluable
rHuPH20 NAb positive ('negative titer'^b or numeric titer value)	Treatment Unaffected rHuPH20 NAb	rHuPH20 NAb unevaluable	titer < 2 x baseline titer: Treatment Unaffected rHuPH20 NAb	titer ≥ 2 x baseline titer: Treatment Boosted rHuPH20 Nab
rHuPH20 NAb not evaluable	rHuPH20 NAb unevaluable	rHuPH20 NAb unevaluable	rHuPH20 NAb unevaluable	rHuPH20 NAb unevaluable

^a Samples with missing titer have as reported rHuPH20 NAb result 'positive immunodepletion' or 'positive titer';

^b Results reported as 'negative titer', ie, titer value <100 will be set to value of 100;

^c Highest sample status, with order: (from low to high): rHuPH20 NAb unevaluable, rHuPH20 NAb negative, rHuPH20 NAb positive (missing titer), rHuPH20 NAb positive with titer <100 ('negative titer' as reported NAb result, titer value set to 100), rHuPH20 NAb positive (ie, actual titer value and selecting the sample with highest titer).

rHuPH20 NAb evaluable participant = participant classified as any of following categories: rHuPH20 NAb negative, treatment-unaffected rHuPH20 NAb, treatment-induced rHuPH20 NAb, treatment-boosted rHuPH20 NAb.

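### An untested antibody-positive sample is outranked by default NAb negatives, so a participant with no NAb result on any antibody-positive post-baseline sample can count as an evaluable NAb negative

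*SAP*

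**What the plan says.** SAP 4.5.2.4 builds the efgartigimod NAb class in four steps.

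- Which samples are assayed: "All ADA confirmed positive samples will also be evaluated in the NAb assay".
- What happens to the rest: "All samples that were not analyzed in the NAb assay (ie, the ADA negatives) are per default NAb negative".
- What happens when a result is lacking: "if a NAb sample is not reported, the NAb sample status is NAb unevaluable".
- How samples are combined after baseline: "Highest sample status in order: (from low to high): NAb unevaluable, NAb negative, NAb positive".

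The combined post-baseline status is crossed with the baseline status in a three-by-three table. Incidence and prevalence both use the "denominator: number of evaluable participants". The definition of who is not evaluable reads: "NAb unevaluable participant = participant classified as NAb unevaluable or with missing baseline NAb sample or without post-baseline NAb samples".

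SAP 4.5.2.5 repeats the default and the order for rHuPH20. The low end of its footnote c runs "rHuPH20 NAb unevaluable, rHuPH20 NAb negative, rHuPH20 NAb positive (missing titer", with the positive categories that carry a titer above that.

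Incidence and prevalence of NAb against efgartigimod and against rHuPH20 are secondary endpoints (protocol section 3, SAP 1.1).

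**The concern.** Only an antibody-positive sample can be NAb positive. If its NAb result is lacking, the participant's NAb status is unknown. The rank order replaces that unknown with a negative taken from samples that never entered the NAb assay. One antibody-negative post-baseline sample is enough, and sampling is repeated over many cycles.

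The definition of an unevaluable participant does not catch the case: the participant has a baseline sample, has post-baseline samples, and has not been classed unevaluable by the table.

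Two things are at stake. Incidence, and in part prevalence, of a secondary endpoint can be understated. The same participants would also sit in the NAb-negative stratum of the efgartigimod NAb correlation tables (serum concentration, total IgG, MG-ADL and adverse events), which SAP 4.5.3 plans by cycle classification.

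The SAP handles a comparable gap differently for ADA. In 4.5.2.2 a positive sample with missing titer ranks above ADA negative. With a baseline titer available, that participant becomes ADA unevaluable even if other post-baseline samples are negative.

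**Working it through.** The plan states no NAb rate, so there is no figure of its own to reproduce. The check has two parts.

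**1. Apply the rules to sample patterns.** U = unevaluable, N = negative, P = positive; the baseline is NAb negative. The last column applies the rule set out in the fix.

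| Post-baseline samples | Statuses | Class as written | Class under the fix |
|---|---|---|---|
| 3 antibody negative | N, N, N | negative/negative, evaluable | unchanged |
| 1 antibody positive untested + 3 antibody negative | U, N, N, N | negative/negative, evaluable | **unevaluable** |
| 1 antibody positive untested, no other sample | U | unevaluable | unchanged |
| 1 antibody positive untested + 1 antibody positive assayed NAb negative | U, N | negative/negative, evaluable | unchanged |
| 1 antibody positive untested + 1 antibody positive assayed NAb positive | U, P | negative/positive | unchanged |

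If the untested sample is the baseline itself, the table already gives unevaluable. If the baseline is NAb positive, the second pattern gives positive/negative, which counts in prevalence but not in incidence. For rHuPH20 the matching class is treatment-unaffected, with the same consequence.

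**2. Bound the effect on the rate.** Let E be the participants evaluable as written, x those classed positive for incidence, k those affected, and j the unknown number of the k who are truly positive.

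- As written: x/E.
- Affected excluded: x/(E − k).
- If j were known: (x + j)/E. The understatement is j/E, at most k/E.
- Upper bound: (x + k)/E.

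E = 201 is the maximum enrolment (SAP 1.3). E = 150 and all values of x and k are assumptions, because the documents give none.

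| E | x | k | As written | Excluded | Upper bound |
|---|---|---|---|---|---|
| 201 | 4 | 1 | 4/201 = 1.99% | 4/200 = 2.00% | 5/201 = 2.49% |
| 201 | 4 | 4 | 4/201 = 1.99% | 4/197 = 2.03% | 8/201 = 3.98% |
| 201 | 4 | 8 | 4/201 = 1.99% | 4/193 = 2.07% | 12/201 = 5.97% |
| 150 | 10 | 5 | 10/150 = 6.67% | 10/145 = 6.90% | 15/150 = 10.00% |
| 150 | 10 | 10 | 10/150 = 6.67% | 10/140 = 7.14% | 20/150 = 13.33% |

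Reclassification alone moves the rate by less than half a percentage point in every row. The gap to the upper bound is larger, and no planned output shows it.

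**The case against.** The case for leaving the rule alone has real substance.

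- **The unevaluable samples are not hidden.** SAP 4.5.3 plans counts of negative, positive and unevaluable samples by visit, repeats them by overall participant class, and extends both to NAb (tables 14.2.6.13, 14.2.6.14, 14.2.6.18 and 14.2.6.19). Listings 16.2.12.1 and 16.2.12.2 cover the individual results, with sample status and participant class. This stands: affected participants can be found. But no planned table counts them, and the planned count of unevaluable participants leaves them out by construction.
- **The correlation tables are only partly exposed.** None uses the rHuPH20 NAb class. The efgartigimod NAb tables need only be produced with at least 5 NAb-positive participants, and the versions by overall class are flagged as not to be created. From year 2 a cycle may hold a single post-baseline sample, and a lone untested sample is already unevaluable. This stands.
- **Results may seldom be missing.** All confirmed positives are meant to be assayed. The remark about samples that cannot be run ("eg, due to insufficient sample volume/quality to perform the titer analysis") concerns titration, not the NAb assay. This stands as to size. Still, 4.5.2.4 itself provides for an unreported NAb result, so the case is foreseen.
- **The order is the SAP's common convention.** Unevaluable ranks below negative in all four classifications. For ADA that is defensible, because every sample enters the screening assay. For NAb the gap falls on the only samples that could be positive.
- **The endpoint is descriptive.** No hypothesis or sample size depends on it. This stands.

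A reader might also infer that every participant with one unreported sample and no NAb-positive sample should be unevaluable. That goes too far: it would discard participants who have another antibody-positive sample actually assayed NAb negative.

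**Conclusion.** The rule as written gives the wrong class in a definable case, and nothing in SAP 4.5.2.4 or 4.5.2.5 reverses it. The case needs three conditions: an evaluable baseline; no NAb result on any antibody-confirmed-positive post-baseline sample, of which there is at least one; and at least one antibody-negative post-baseline sample in the same period.

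The understatement of incidence is at most affected/evaluable participants. Prevalence is exposed only when the baseline is NAb negative. The number affected is not in the documents and may be small or zero, so the percentages above only illustrate scale.

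A reader might infer that NAb incidence and prevalence are biased downward by a known factor, or that the gap is concealed. The documents support neither. They give no ADA rate, NAb rate or share of missing results; prevalence is unaffected with a NAb-positive baseline; and the unevaluable samples are tabulated and listed. What is missing is the correct class, a count of the participants concerned, and the range that the count implies.

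**What to change.** In SAP 4.5.2.4 and 4.5.2.5, add one rule to the derivation. It applies separately within each period being classified (each cycle, and overall). If the participant has antibody-confirmed-positive post-baseline samples, none of them has a reported NAb result, and there is therefore no NAb-positive sample, class the participant NAb unevaluable, however many default-negative samples there are. State that participants with at least one antibody-positive sample assayed NAb negative keep their present class.

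In the NAb classification tables (14.2.6.16 and 14.2.6.20), print the number of participants reclassified by this rule. Give incidence with them excluded and, as an upper bound, counted as positive.

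The cost is one derivation rule in each of two sections, one count and one extra rate. The sample-level statuses are already derived. The evaluable denominator becomes slightly smaller and the reported rate may be slightly less favourable.

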4.5.2.2 PARTICIPANT CLASSIFICATION FOR ADA AGAINST EFGARTIGIMOD

Table below gives an overview of how the ADA participant classification will be derived, starting from the participant baseline ADA sample status.

Participant ADA classification	Highest ^c post baseline sample status			
	ADA negative	ADA positive (missing titer ^a)	ADA positive ('negative titer' ^b or numeric titer value)	ADA not evaluable
ADA negative	ADA negative	Treatment Induced ADA	Treatment Induced ADA	ADA unevaluable
ADA positive (missing titer ^a)	Treatment Unaffected ADA	ADA unevaluable	ADA unevaluable	ADA unevaluable
ADA positive ('negative titer' ^b or numeric titer value)	Treatment Unaffected ADA	ADA unevaluable	titer < 4 x baseline titer: Treatment Unaffected ADA	titer ≥ 4 x baseline titer: Treatment Boosted ADA ^d
ADA not evaluable	ADA unevaluable	ADA unevaluable	ADA unevaluable	ADA unevaluable

^a Samples with missing titer have as reported ADA result 'positive immunodepletion' or 'positive titer';

^b Results reported as 'negative titer', ie, titer value <1 will be set to value of 1;

^c Highest sample status, with order: (from low to high): ADA unevaluable, ADA negative, ADA positive (missing titer/positive immunodepletion), ADA positive with titer ≤ 1 ('negative titer' as reported ADA result, titer value set to 1), ADA positive with titer > 1 (ie, positive titer and selecting the sample with highest titer)

^d Note: Fourfold difference in titer values is considered significant in case a twofold serial dilution is applied (= two times the dilution factor) (reference to Shankar et al., 2014).

ADA evaluable participant = participant classified as any of following categories: ADA negative, treatment-unaffected ADA, treatment-induced ADA, treatment-boosted ADA.

ADA unevaluable participant = participant classified as ADA unevaluable or with missing baseline ADA sample or without post-baseline ADA samples

In case no ADA data is available at all, the participant can not be classified.

ADA incidence = percentage of participants with treatment-induced or treatment-boosted ADAs (denominator: number of evaluable participants).

ADA prevalence = percentage of participants with treatment-unaffected ADA, treatment-induced ADA or treatment-boosted ADA (denominator: number of evaluable participants).

	Statistical Analysis Plan	
ARGX-113-2002	Final Analysis	Final 5.0 of 31Jan2025

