Anti-rHuPH20 Ab incidence = percentage of participants with treatment-induced or treatment-boosted rHuPH20 Ab (denominator: number of evaluable participants).

Anti-rHuPH20 Ab prevalence = percentage of participants with treatment-unaffected rHuPH20 Ab, treatment-induced rHuPH20 Ab or treatment-boosted rHuPH20 Ab (denominator: number of evaluable participants).

	Statistical Analysis Plan	
ARGX-113-2002	Final Analysis	Final 5.0 of 31Jan2025

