rHuPH20 NAb unevaluable participant = participant classified as rHuPH20 NAb unevaluable or with missing baseline rHuPH20 NAb sample or without post-baseline rHuPH20 NAb samples

In case no rHuPH20 NAb data is available at all, the participant can not be classified.

Anti-rHuPH20 NAb incidence = percentage of participants with treatment-induced or treatment-boosted rHuPH20 NAb (denominator: number of evaluable participants).

Anti-rHuPH20 NAb prevalence = percentage of participants with treatment-unaffected rHuPH20 NAb, treatment-induced rHuPH20 NAb or treatment-boosted rHuPH20 NAb (denominator: number of evaluable participants).

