The duration of ADA response against Efgartigimod will also be tabulated during the pre-amended treatment + follow-up phase by presenting the number of consecutive and number of total cycles of treatment induced or boosted ADA in ADA positive participants during that phase. This analysis will also be done for rHuPH20 Ab.

	Statistical Analysis Plan	
ARGX-113-2002	Final Analysis	Final 5.0 of 31Jan2025

Correlation tables by ADA and NAb participant classification against efgartigimod, and by rHuPH20 Ab participant classification will be provided for the following parameters:

- mean drug concentration over time
- mean percent change from baseline in total IgG
- mean changes from baseline in total MG-ADL
- treatment-emergent adverse events
- serious treatment-emergent adverse events
- injection-related reactions (see Section 5.1.2)
- injection site reactions (see Section 5.1.2)

For final analysis, correlation tables will be prepared showing the cycle participant classification for the total treatment group.

Correlation tables by cycle NAb against efgartigimod participant classification only need to be provided as soon as there are at least 5 participants in the sum of baseline negative – postbaseline positive and baseline positive – postbaseline positive (NAb positive categories) in (one of) the treatment arms.

All available data on ADA and NAb against efgartigimod, rHuPH20 Ab and rHuPH20 NAb will be listed, showing also the sample status and participant classification.

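### SAP 4.5.2.4 counts participants who are NAb-positive both at the 2002 baseline and afterwards as incident efgartigimod NAb cases, while the SAP's other three incidence definitions count a baseline positive only when a titer boost is shown

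*SAP*

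**What the plan says.** SAP 4.5.2.4 cross-classifies each participant by NAb status at baseline and by the highest status seen after baseline. The incidence rule then takes two of the four evaluable cells: "NAb incidence = percentage of participants with participant classification ‘baseline neg – post-baseline pos’ and ‘baseline pos – post-baseline pos". Prevalence adds the one remaining cell with a positive sample: "NAb prevalence = percentage of participants with participant classification ‘baseline neg – post-baseline pos’, ‘baseline pos – post-baseline pos’ or ‘baseline pos – post-baseline neg".

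The other three antibody measures follow a different rule:

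- Efgartigimod ADA (SAP 4.5.2.2): "ADA incidence = percentage of participants with treatment-induced or treatment-boosted ADAs (denominator: number of evaluable participants".
- rHuPH20 antibodies (SAP 4.5.2.3): "Anti-rHuPH20 Ab incidence = percentage of participants with treatment-induced or treatment-boosted rHuPH20 Ab (denominator: number of evaluable participants".
- rHuPH20 NAb (SAP 4.5.2.5): "Anti-rHuPH20 NAb incidence = percentage of participants with treatment-induced or treatment-boosted rHuPH20 NAb (denominator: number of evaluable participants".

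In those three, a baseline positive needs a titer rise to count as boosted. For efgartigimod ADA the threshold is fourfold ("titer ≥ 4 x baseline titer: Treatment Boosted ADA"); for both rHuPH20 measures it is twofold. Without that rise the participant is treatment-unaffected and enters prevalence only.

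On the efgartigimod NAb assay, SAP 4.5.1 says: "For NAb against efgartigimod, a screening assay is performed and results will be reported as negative or positive". There is no titration step for this measure.

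**The concern.** Incidence should describe antibodies that arise, or clearly increase, during the study. Under 4.5.2.4 a participant whose NAb status is positive at baseline and still positive later is reported as a case arising in this study, although nothing has been shown to change.

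Baseline positives are a realistic possibility. Everyone enters from ARGX-113-2001 or ARGX-113-1705, where efgartigimod was given (Protocol 4.1), and the baseline is the last value before the first dose in this study (SAP 2.2.2), not a drug-naive value. SAP 4.5.3 applies the 2002 baseline to both cycle-level and overall classifications of ADA and rHuPH20 antibodies and then repeats the tables for NAb. A carried-over positive could therefore be counted as incident again in each cycle in which it tests positive.

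Incidence of NAb against efgartigimod is a named secondary endpoint (Protocol Section 3; SAP 1.1). At stake is a reported rate that carries the wrong label and cannot be read beside the other three incidence rates in the same section.

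**Working it through.** The plan states no figure for this point, so there is nothing to reproduce. The check compares the definitions cell by cell and then sizes the difference.

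**Step 1. What each rule does with a participant who is positive after baseline.**

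| Measure (SAP section) | Baseline negative | Baseline positive, rise below threshold | Baseline positive, rise at or above threshold | Baseline positive, rise cannot be judged |
|---|---|---|---|---|
| Efgartigimod ADA (4.5.2.2) | incident | not incident | incident (≥ 4×) | unevaluable |
| rHuPH20 antibodies (4.5.2.3) | incident | not incident | incident (≥ 2×) | unevaluable |
| rHuPH20 NAb (4.5.2.5) | incident | not incident | incident (≥ 2×) | unevaluable |
| Efgartigimod NAb (4.5.2.4) | incident | no titer | no titer | **incident** |

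For efgartigimod NAb every baseline positive falls in the last column, because the assay is only positive or negative. Elsewhere the SAP never calls that situation incident.

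**Step 2. What the efgartigimod NAb rule measures.** By baseline/post-baseline cell:

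- neg/neg: neither incident nor prevalent
- neg/pos: incident and prevalent
- pos/neg: prevalent only
- pos/pos: incident and prevalent

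So the SAP's incidence equals any post-baseline positivity and differs from its prevalence only by the pos/neg cell. SAP 4.5.3 uses the same total as the trigger for the NAb correlation tables and describes it as "the sum of baseline negative – postbaseline positive and baseline positive – postbaseline positive (NAb positive categories".

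**Step 3. Coherence with ADA.** NAb is assayed only on confirmed ADA-positive samples. Take a participant with the same ADA titer and a positive NAb result at and after baseline. Under 4.5.2.2 this is treatment-unaffected ADA, not incident. Under 4.5.2.4 it is an incident NAb case. NAb incidence could therefore exceed ADA incidence through carry-over alone.

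**Step 4. Size.** Let a = number neg/pos, b = number pos/pos, k = number of the b who are truly boosted (not observable), N = NAb-evaluable participants.

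- SAP incidence = (a + b)/N
- Newly positive incidence = a/N, so the excess is b/N
- Induced-or-boosted incidence = (a + k)/N, so the excess is (b − k)/N, which lies between 0 and b/N

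Input from the documents: N ≤ 201 (SAP 1.3). The values of a and b are assumptions, because the documents give no NAb counts. With N = 201 and a = 5:

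| b | SAP incidence | Newly positive | Excess (points) |
|---|---|---|---|
| 0 | 5/201 = 2.5% | 2.5% | 0 |
| 2 | 7/201 = 3.5% | 2.5% | 1.0 |
| 5 | 10/201 = 5.0% | 2.5% | 2.5 |
| 10 | 15/201 = 7.5% | 2.5% | 5.0 |

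One pos/pos participant adds 1/201 = 0.50 points at the largest possible N, and more at any smaller N. Put the other way, if a + b = 5 and N = 201, the SAP reports 2.5% whatever the split, while the newly positive rate could be anything from 0% to 2.5%.

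**The case against.** The case for leaving the rule alone has five parts.

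1. **The cells are reported anyway.** Tables 14.2.6.16 and 14.2.6.17 show the participant classification beside incidence and prevalence, and Listing 16.2.12.1 gives individual data, so a reader can recover a/N by subtraction. This is true and limits the harm, but the printed rate would still be mislabelled.
2. **Without a titer both rules are bounds.** The SAP's rule includes every possible boost, and the proposed rule includes none. This is also true, and the documents do not show which bound is closer. But the SAP does not present its rate as an upper bound, gives no reason for the choice (Section 6 does not mention it), and takes the opposite line for the other three measures when a boost cannot be judged.
3. **The fix does not make the four rates identical.** Efgartigimod NAb would be induced-only, the others induced-or-boosted, and the thresholds already differ (4× and 2×). This stands, and is why a footnote is needed.
4. **Following the SAP's own analogy strictly, pos/pos participants would be unevaluable** and would leave the denominator and prevalence as well. The fix is indeed a new rule. It keeps them because their NAb status is known at both times; only the boost is unknown.
5. **The stakes are modest.** The endpoint is descriptive, the study tests no hypothesis, NAb positivity needs a confirmed ADA-positive sample, and the effect may be zero. This argues against a grade above should-fix. It does not make the label right.

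**Conclusion.** The concern holds. As written, SAP 4.5.2.4 reports any post-baseline NAb positivity under the name of incidence, and it departs from the SAP's other three incidence definitions without explanation. Only pos/pos participants are affected; those positive at baseline and negative throughout afterwards are not counted as incident.

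The excess over newly positive participants is b/N. It is zero if nobody is positive at both times and otherwise at least 0.50 percentage points per such participant, resting on the enrolment cap of 201. The excess over an induced-or-boosted rate lies between 0 and b/N and cannot be determined without a titer. All values of a and b used above are assumptions. This should be fixed because a reported secondary endpoint changes, but no test, sample size or primary safety endpoint depends on it.

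**What to change.** In SAP 4.5.2.4:

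- Define incidence as the neg/pos cell only, over the NAb-evaluable participants already used as the denominator there.
- Report the pos/pos cell on its own line as baseline-positive with boost not determinable, counted in prevalence only.
- Add a footnote that any truly boosted baseline positives are not counted as incident because the assay gives no titer.
- If the sum of the two cells is still wanted, keep it under the label of any post-baseline NAb positivity.

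Apply this to Tables 14.2.6.16 and 14.2.6.17.

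The cost is one line of SAP text, one derivation flag and one footnote; no new samples or assays are needed. The downside is a possible under-count relative to induced-or-boosted incidence, of k/N, which the footnote must make plain.
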